	
RRT free days at D30
 
 • Nature and frequency of adverse events • Evolution of FX06 concentration from H0 to H1, measured at time 0 (before FX06 application) and after 5, 15, 30, 60 min • PK/PD analysis will be performed from those dosages, with a reduction of EVLWi of more than 30% before and 3 hours after injection as primary PD endpoint at day 2 • Immunogenicity of the drug will be tested at day 7, according to manufacturer's procedure (cf 5.7) 
Exploratory objectives will be:
 
 - To characterize responder patients (defined as patient with a change in extravascular lung water index between D1 and Day 7 after inclusion > 30%) - To study the prognosis (overall mortality) of responder patients (defined as patient with a change in extravascular lung water index between D1 and Day 7 after inclusion > 30%).
Design of the study	Comparative, double-blinded, controlled (1:1), randomized trial, assessing the effect of FX06 infusion on the top of standard of care vs standard of care alone in 2 parallel arms, and multicentric (3 ICUs from three different hospitals).
Population of study participants	Patients admitted in participating ICUs who received mechanical ventilation for SARS-CoV-2 induced acute respiratory distress syndrome (ARDS)
Inclusion criteria	
 1. Age \geq 18 years 2. SARS-CoV-2 induced pneumonia confirmed by a positive PCR test in nasopharyngeal swab or respiratory tract secretions 3. Acute respiratory distress syndrome (ARDS) according to Berlin criteria (bilateral pulmonary infiltrates on frontal chest x-ray, PaO₂/FiO₂ ratio \leq300 mmHg, objective assessment excluding hydrostatic pulmonary edema) 4. Need for endotracheal intubation and mechanical ventilation 5. Informed consent by patient or legal representative. According to the specifications of emergency consent, randomization without the close relative or surrogate consent could be performed. 6. Affiliated to a social security system 7. Highly effective method of contraception and negative highly sensitive pregnancy test, for women of childbearing potential

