4.1.2 Secondary endpoints

- Evolution of daily extravascular lung water index (EVLWi), cardiac index, global end-diastolic volume index, pulmonary vascular permeability index, measured by transpulmonary thermodilution during 7 days.
- Overall survival at 30 days
- Mortality rate in ICU, in hospital
- Rate of withdraw or withhold life-sustaining treatments decision at Day 30
- Vascular leak:
 - Daily weight until D7 (% of D1)
 - Daily fluid balance until D7
 - Evolution of albuminemia until D7
- Pulmonary recovery:
 - Duration of mechanical ventilation (MV) and MV free days at D30
 - Ventilator-free survival (proportion of participants alive and off invasive mechanical ventilation) at D30
 - PaO₂/FiO₂ and Murray ARDS severity score over 15 days
 - Evolution of pulmonary SOFA score over 15 days
 - Evolution of radiological Weinberg score over 30 days, analysed by a specialized radiologist, blinded for the treatment group
 - Rate of rescue therapy with VV-ECMO
- Evolution of daily sequential organ failure score (SOFA) and organ failure (one or more SOFA sub-score ≥3) failure free days at D15
- Hemodynamic parameters
 - systolic, diastolic, mean blood pressure, heart rate twice a day during 7 days
 - lactate clearance, measured once a day during 7 days
 - catecholamine-free days at D30
- Duration of renal replacement therapy (RRT), and RRT free days at D30
- Nature and frequency of adverse events
- Evolution of FX06 concentration from H0 to H1, measured at time 0 (before FX06 application) and after 5, 15, 30, 60 min
- PK/PD analysis will be performed from those dosages, with a reduction of EVLWi of more than 30% before and 3 hours after injection as primary PD endpoint at day 2
- Immunogenicity of the drug will be tested at day 7, according to manufacturer's procedure (cf 5.7)

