 - Positive end-expiratory pressure (PEEP)
 - Plateau pressure
 - FiO₂
 - Level of catecholamines: inotrope score, calculated as IS= dose of dubutamine (µg/kg/min)+ 100 x [dose of norepinephrine (µg/kg/min) + dose of epinephrine (µg/kg/min)] [16]
 - Supplementation by hydrocortisone Y/N
 - Biological exams :

- Arterial blood gases
 - Haematology (blood count)
 - Ionogram, renal and hepatic markers
 - serum glucose, CRP, LDH, NT-pro-BNP, procalcitonin, troponin
 - Coagulation tests: PT ratio, aPTT, Fibrinogenemia, D-Dimers
 - Albuminemia
 - ECG
 - SOFA score
 - RRT or not
 - Chest x-ray
 - Trans-thoracic echocardiography
- Assessment of transpulmonary thermodilution (TPT) parameters. **One measurement will be made before administration of the treatment [7]. All parameters will be evaluated in supine position. Parameters recorded will be: Extra-vascular lung water index, Global end-diastolic volume index, pulmonary vascular permeability index, and cardiac index.** Central venous and arterial lines used for the routine care of the patient will be compatible with TPT systems (either PICCO, Getinge, Germany or EV1000, Edwards Lifesciences, US).
- Treatment
 - Administration by IV perfusion 400mg FX06 intravenously or placebo as a two-time bolus within 10 minutes interval)
 - Administration as soon as possible after randomization, but no longer than 12 hours.
- Pharmacokinetic study: Additional 1 ml blood sample will be taken at time 0 (before FX06 application) and after 5, 15, 30, 60 min. Because FX06 in blood is quickly degraded by endopeptidases, the following sampling procedure should be followed: 1 ml blood to be collected into tubes containing Li-heparin, mixed by inversion 10 times, and then 0.8 ml of this blood to be transferred to test tubes containing 0.08 ml of 0.88 M HCl. It is critical that blood is being transferred to acid within 2 min of collection. The tubes are closed, the acidified blood samples will be mixed by inversion 10 times, and then processed to plasma by centrifugation (2500g; 10 min). Acidified plasma samples will be stored at a temperature of less than -20°C. FX06 dosage will be processed according by F4-Pharma, according to its dedicated procedure. Alternatively, pharmacokinetic study may be performed every other day of treatment (D1 to D5).

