5.2 Follow-up visits

5.2.1 D2 to D5 (all data recorded at 10 O’Clock in the morning)

- Vital status
 - Weight of the patient
 - Daily fluid balance
 - Co-infection or not
 - Specific treatment received for SARS-CoV-2 (CTC, Remdesivir)
 - Diuretics
 - RRT or not
 - Ongoing prone-positioning (prone positioning on the day on the evaluation)
 - Standard clinical monitoring (arterial pressure, heart rate)
 - Ventilatory settings:
 - VV-ECMO Y/N
 - Ventilatory mode (ACV, PSV, APRV, spontaneous breathing)
 - Tidal volume
 - Respiratory rate
 - Positive end-expiratory pressure (PEEP)
 - Plateau pressure
 - FiO₂
 - Level of catecholamines: inotrope score, calculated as IS= dose of dobutamine (µg/kg/min)+
-

- 100 x [dose of norepinephrine ($\mu\text{g}/\text{kg}/\text{min}$) + dose of epinephrine ($\mu\text{g}/\text{kg}/\text{min}$)] [16]
 - Supplementation by hydrocortisone Y/N
 - Biological exams:
 - o Arterial blood gases
 - o Haematology (blood count)
 - o Ionogram, renal and hepatic markers
 - o serum glucose, CRP, LDH, NT-pro-BNP, procalcitonin, troponin
 - o Coagulation tests: PT ratio, aPTT, fibrinogenemia, D-Dimers
 - o Albuminemia
 - ECG
 - Use of renal replacement therapy
 - SOFA score
 - Chest x-ray
 - Trans-thoracic echocardiography
- Assessment of transpulmonary thermodilution (TPT) parameters. **Two measurements will be made, one before administration of the treatment, and one 3 hours after at day 2 [7].** For day 3 to D5, one measurement will be made before administration of the treatment. **All parameters will be evaluated in supine position. Parameters recorded will be: Extra-vascular lung water index, Global end-diastolic volume index, pulmonary vascular permeability index, and cardiac index.** Central venous and arterial lines used for the routine care of the patient will be compatible with TPT systems (either PICCO, Getinge, Germany or EV1000, Edwards Lifesciences, US).
 - Treatment
 - Administration by IV perfusion (400mg FX06 intravenously or placebo as a two-time bolus within 10 minutes interval)

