5.6 Table or diagram summarising the chronology of the study

Actions	D1	D2 to D5	D6 to D7	D8, D10, D15, ICU discharge, death	D30	D60
Information	X					
Signature of the consent form from a close relative or surrogate, or emergency consent form	X					
Randomization	X					
Administration of study drug or placebo	X	X				
Pharmacokinetic study	X					
Medical history	X					
Clinical exam	X					
Co-infection or not	X	X	X			

Weight	X	X	X			
Fluid balance		X	X			
EVLWI measured by TPT (primary endpoint)		X	X			
Standard clinical monitoring	X	X	X			
Ventilatory settings	X	X	X	X		
Doses of catecholamines	X	X	X	X		
Arterial blood gases	X	X	X	X*		
Blood pregnancy test	X				X	
NFS, TP, TCA, fibrinogen, D-Dimers	X	X	X			
Electrolytes, creatinemia, serum glucose, CRP, LDH, NT-pro-BNP, procalcitonin, troponin	X	X	X			
ECG	X	X	X			
Liver tests	X	X	X			
Albuminemia	X	X	X			
SOFA score	X	X	X	X		
RRT or not	X	X	X	X	X	
TTE	X	X	X (D7)			
Chest X-RAY	X	X	X	X*	X*	
Adverse events		X	X	X	X	
Pursuit consent		X	X	X	X	
Vital status					X	
Withhold life-sustaining treatments decision					X	
Ventilator-free survival					X	
Secondary pneumonia, nb of episodes					X	
Rescue therapy with VV-ECMO					X	
Catecholamine-free days at D30					X	
RRT free days at D30					X	
Serum sample for immunogenicity and IL6 measurement			X (D7)			
Prescription of a highly effective method of contraception for three months (for women of childbearing potential)				X (ICU discharge)		
Patient's status						X

*, if clinically indicated

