5.7 Distinction between standard care and study

Procedures and treatments carried out as part of the research	Procedures and treatments associated with care	Procedures and treatments added because of the research
Treatments	Standard of care	FX-06 administration or its placebo at D1, D2, D3, D4, D5
Consultations	D1 to D30: During patient's hospitalisation's	Follow up by phone: at D30 and D60 in case of discharge from the ICU
Blood samples	Haematology - Biochemistry	Day 1 : 1 ml at time 0 (before FX06 application) and after 5, 15, 30, 60 min Day 7 : 3 ml serum
Imaging, etc.	TTE Chest X-Rays ECG	None
Monitoring	Transpulmonary thermodilution technique	

Particularly, transpulmonary thermodilution technique is part of the routine monitoring during ARDS [15].

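### FX06 is sampled around the Day 1 dose but the primary PD response is read around the Day 2 dose, so no dose has both under the base schedule

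*Protocol*

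**What the plan says.** Section 3.2 of the protocol makes the PK/PD parameters of FX06 a study objective. Section 4.1.2 lists FX06 concentrations at 0, 5, 15, 30 and 60 min. It then ties the analysis to these samples ("PK/PD analysis will be performed from those dosages") and defines the response to be related to them in these terms: "with a reduction of EVLWi of more than 30% before and 3 hours after injection as primary PD endpoint at day 2". The Summary (section 1) repeats this.

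The schedule is set out elsewhere:

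- **FX06 concentrations.** Section 5.1 lists the sampling under the D1 visit. In the 5.6 table, the row "Pharmacokinetic study" is marked at D1 only. Section 5.7 gives the added blood samples as "Day 1 : 1 ml at time 0 (before FX06 application) and after 5, 15, 30, 60 min". Section 5.8 repeats the procedure and names no day.
- **EVLWi on D1.** Section 5.1: "One measurement will be made before administration of the treatment". No post-dose reading is planned that day.
- **EVLWi on D2.** Section 5.2.1: "Two measurements will be made, one before administration of the treatment, and one 3 hours after at day 2". D3 to D5 have one pre-dose reading each, and D6 and D7 (section 5.2.2) one reading a day after treatment has ended.
- **Optional sampling.** Section 5.1 adds: "Alternatively, pharmacokinetic study may be performed every other day of treatment (D1 to D5"). Sections 5.6 and 5.7 do not carry this option.

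**The concern.** An exposure–response analysis is most direct when the concentration and the response belong to the same dose. Here the concentrations describe dose 1, while the response chosen as the primary PD endpoint follows dose 2. The reference value for that response is the D2 pre-dose reading, taken after dose 1, so it is not a drug-free baseline.

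This is a phase IIa trial in which the PK/PD relation is a named objective. Sampling days are fixed in the protocol, and a later analysis plan cannot supply a concentration or a reading that was never taken. Without a change, the PK/PD result rests on an assumption that the protocol does not state and the base schedule cannot test: that each patient's exposure on Day 2 equals that on Day 1.

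**Working it through.** No stated figure is in dispute here; the check sets the two schedules side by side.

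**Step 1. Measurements by dose, base schedule (5.1, 5.2.1, 5.6, 5.7)**

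| Dose | FX06 at 0–60 min | EVLWi pre-dose | EVLWi at 3 h |
|---|---|---|---|
| D1 | yes | yes | no |
| D2 | no | yes | yes |
| D3 | no | yes | no |
| D4 | no | yes | no |
| D5 | no | yes | no |

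The sampling days are {1} and the days with a 3-hour reading are {2}. They do not overlap: 0 of 5 doses have both. Dose 1 has concentrations, plus EVLWi before dose 1 and before dose 2, but not the 3-hour value on which the endpoint is defined.

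**Step 2. The optional sampling sentence in 5.1**

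- Read as D1, D3, D5: {1, 3, 5} against {2}, overlap 0 of 5.
- Read as D2, D4: {2, 4} against {2}, overlap 1 of 5.
- Read as any day from D1 to D5: overlap 1 of 5, and only if D2 is chosen.

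The option can reach D2 on some readings. It fixes D2 on none, because it is worded as a permission.

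**Step 3. Number of samples**

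The protocol plans 25 patients per group (12.2). That figure reproduces from its own inputs: difference 0.30 × 13.4 = 4.02, SD 5, 80% power, two-sided 5%, giving n = 25 per group (power 0.811 by the normal approximation). It is used here only for counting.

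- Active arm: 25 × 5 = 125 concentrations.
- Both arms: 50 × 5 = 250. The placebo half contains no FX06, so 125 is the relevant count.
- Concentrations taken at the dose whose 3-hour response is the endpoint: 0.

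**Step 4. Can the same-exposure assumption be checked?**

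Degrees of freedom for dose-to-dose variation within FX06 patients = 25 × (occasions − 1).

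- One occasion (base schedule): 25 × 0 = 0.
- Two occasions (D1 and D2): 25 × 1 = 25, if all 25 patients complete both sets.

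**Step 5. Burden, for costing a change**

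- Thermodilutions per patient: D1 1 + D2 2 + D3–D5 3 + D6–D7 2 = 8, or 400 over 50 patients. One added reading gives 9, or 450.
- Blood: 5 × 1 ml = 5 ml per set, 10 ml if the set is repeated.

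**The case against.** The strongest reply is that a PK/PD analysis does not need both measurements on one dose. A patient's exposure estimate can be linked to a later response. The dose is the same 400 mg each day, given the same way (7.1.1), and the protocol describes FX06 as rapidly broken down in blood (5.1, 5.8), so carry-over is less likely and Day 1 exposure may be a fair proxy for Day 2. Nothing in the protocol shows that it is not. How concentrations are to be linked to EVLWi may also be left to an analysis plan, and daily EVLWi readings allow other PD measures. Finally, the optional sentence in 5.1 leaves a route to D2, and the whole matter concerns one secondary objective.

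Much of this stands. The analysis is weakened, not impossible, and no bias of known size can be shown. Three things remain:

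- The proxy assumption is not written down, and the base schedule cannot test it. These are intensive-care patients whose weight, fluid balance and renal replacement status are followed daily. The interval between doses 1 and 2 is also not fixed, since dose 1 may be given up to 12 hours after randomisation (5.1). Recorded administration times (7.3) let that interval be described but do not replace a concentration.
- An analysis plan can choose how to link the data but cannot create the missing measurement.
- The optional sentence does not require D2 sampling and is absent from the schedule table and the list of added procedures.

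**Conclusion.** The point holds. Under the base schedule, 0 of 5 doses have both the 0–60 min FX06 concentrations and the 3-hour EVLWi reading that defines the primary PD endpoint. The optional schedule raises this to 1 of 5 at most, and only on a reading that includes D2.

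The consequence is confined to the secondary PK/PD objective, which would rest on an untested assumption of equal exposure at doses 1 and 2. The primary D1–D7 comparison, the sample size and the dosing are unaffected. The conclusion depends only on the protocol's schedule; the sample counts also assume 25 treated patients with complete sets. The schedule should be changed, because the loss cannot be made good afterwards and the change is small.

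**What to change.** Put the concentrations and the 3-hour response on the same dose.

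**Preferred: keep the Day 2 pair and fix FX06 sampling at the Day 2 dose.** Either move the 0–60 min set from D1 to D2 or, better, take it on both days. No extra thermodilution is needed. Blood volume is unchanged if the set is moved and rises from 5 to 10 ml per patient if it is repeated, with a second round of the sample handling that requires transfer to acid within 2 minutes. Repeating the set also gives up to 25 degrees of freedom for comparing exposure on the two days.

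**Alternative: take a 3-hour EVLWi after the Day 1 dose and make the Day 1 pair the primary PD endpoint.** Its reference value would precede any FX06, and no extra blood is needed. Thermodilutions stay at 8 per patient if the D2 3-hour reading is moved and rise to 9 if one is added (400 to 450 over 50 patients). The drawbacks are practical. Dose 1 has no fixed clock time, so the reading may fall at night. It must also be supine, and a prone session of at least 16 h (7.4) leaves at most 24 − 16 = 8 h supine in a day, so some readings may be missed; the Day 2 pair shares this last limit. The alternative also changes the question to a first-dose response.

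In either case, replace the optional sentence in 5.1 with named sampling days, carry them through 4.1.2, 5.2.1, 5.6 and 5.7, and state the day in 5.8. Use the administration times recorded under 7.3 to describe the interval between doses. Dosing, the Day 7 assessment and the primary analysis do not change.

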4.2 Description of research methodology

4.2.1 Design of the study

Comparative, double-blinded, controlled (1:1), randomized trial, assessing the effect of FX06 infusion on the top of standard of care vs standard of care alone in 2 parallel arms, and multicentric (3 ICUs from three different hospitals).

4.2.3 Identification of participants

The subjects participating in this study will be identified as follows:

Site number (3 digits) - Sequential selection number for the site (4 digits) - surname initial - first name initial

This reference number is unique and will be used for the entire duration of the trial.

A randomisation number will also be assigned when the participant is randomised. This number will have the following format: XXX.

A treatment number, formatted as T0000 (1 letter and 4 numbers), will be also assigned when the participant is allocated to a treatment arm.

4.2.4 Randomisation

The randomization list will be computer-generated and stratified according to each ICU.

Patients will be randomly assigned in a 1:1 ratio to FX06 or standard of care.

Concealment of the study-group assignments is achieved with the use of a centralized, secure, interactive, Web-based response system (CleanWeb, Telemedicine Technologies) accessible from each study center.

After each randomization, a treatment number is allocated to the patient and a confirmation email of randomization is sent automatically to the investigator concerned and the URC.

4.2.5 Blinding methods and measures put in place to protect blinding

This study will be conducted in a blinded fashion. To maintain blinding of study treatment, unrecognizable study medications (numbered and sealed Therapeutic Units = boxes containing 10 vials of active or placebo solution) will be prepared.

Subjects, Investigators and the Sponsor's staff conducting the study, will not have access to individual subject treatment assignments. The Randomization Center will have access to such assignments. Blinding is critical to the integrity of this clinical study. However, in the event of a medical emergency or pregnancy in an individual subject, in which knowledge of the investigational product is critical to the subject's management, the blind for that subject may be broken by the treating investigator.

Before breaking the blinding of an individual subject's treatment, the investigator should have determined that the information is necessary, i.e. that it will alter the subject's immediate management. In many cases, particularly when the emergency is clearly not investigational product-related, the problem may be properly managed by assuming that the subject is receiving active product without the need for unblinding.

4.2.6 Unblinding procedures

Unblinding will be requested for any reason considered essential by the investigating doctor by calling upon:

- **In emergency cases** at the poison control center at Fernand Widal Hospital, [contact]**. In the case of unblinding the Sponsor will be informed immediately.
 - **Apart from an emergency situation** at the CRID with the CRID project advisor whose contact information is listed on the protocol cover page. The request should be addressed on working days and during working hours.
-

5 IMPLEMENTATION OF THE STUDY

5.1 Baseline visit = randomisation visit = D1

Informed consent will be obtained by investigator of each center from a close relative or surrogate. When such a person will be absent, the patient will be randomized according to French law specifications for emergency consent and patient's surrogate will be asked to give his or her consent for continuation of the trial, and the patient's himself when his or her condition will allow it permitted.

Inclusion and exclusion criteria will be verified by each investigator before inclusion, using a web based questionnaire, blood pregnancy test will be performed (if applicable) and the patient will be randomized through a web-based procedure.

Whose consent must be obtained	Who informs the individual and collects their consent	When is the individual informed	When is the individual's consent collected

 • Patient's legal representative, family member or a close relative 	
 • Local site investigator 	
 • For patient's legal representative, family member or close relative : Before randomization OR as soon as possible after randomisation • For patient: When his/her condition will allow 	
 • For patient's legal representative, family member or close relative : Before randomization OR as soon as possible after randomisation • For patient: When his/her condition will allow

- Demographic and usual clinical data will be extracted from medical charts.
 - Date of inclusion in the FX-COVID study
 - Demographic data: Age, sex, Weight and size, Charlson and Mc Cabe scores, previous medical condition (Diabetes, ischemic cardiomyopathy, cardiac insufficiency, renal insufficiency, chronic dialysis, chronic respiratory insufficiency, COPD, liver cirrhosis, cancer, Immunocompromized, other)
 - Symptoms duration before inclusion
 - Specific treatment received for SARS-CoV-2 before inclusion (CTC, Remdesivir)
 - Diuretics
 - Duration of mechanical ventilation before inclusion
 - Co-infection or not
 - Weight of the patient
 - Ongoing prone-positioning (prone positioning on the day on the evaluation)
 - Standard clinical monitoring (arterial pressure, heart rate)
 - Ventilatory settings :
 - VV-ECMO Y/N
 - Ventilatory mode (ACV, PSV, APRV, spontaneous breathing)
 - Tidal volume
 - Respiratory rate
 - Positive end-expiratory pressure (PEEP)
 - Plateau pressure
 - FiO₂
 - Level of catecholamines: inotrope score, calculated as IS= dose of dubutamine (µg/kg/min)+ 100 x [dose of norepinephrine (µg/kg/min) + dose of epinephrine (µg/kg/min)] [16]
 - Supplementation by hydrocortisone Y/N
 - Biological exams :

- Arterial blood gases
 - Haematology (blood count)
 - Ionogram, renal and hepatic markers
 - serum glucose, CRP, LDH, NT-pro-BNP, procalcitonin, troponin
 - Coagulation tests: PT ratio, aPTT, Fibrinogenemia, D-Dimers
 - Albuminemia
 - ECG
 - SOFA score
 - RRT or not
 - Chest x-ray
 - Trans-thoracic echocardiography
- Assessment of transpulmonary thermodilution (TPT) parameters. **One measurement will be made before administration of the treatment [7]. All parameters will be evaluated in supine position. Parameters recorded will be: Extra-vascular lung water index, Global end-diastolic volume index, pulmonary vascular permeability index, and cardiac index.** Central venous and arterial lines used for the routine care of the patient will be compatible with TPT systems (either PICCO, Getinge, Germany or EV1000, Edwards Lifesciences, US).
- Treatment
 - Administration by IV perfusion 400mg FX06 intravenously or placebo as a two-time bolus within 10 minutes interval)
 - Administration as soon as possible after randomization, but no longer than 12 hours.
- Pharmacokinetic study: Additional 1 ml blood sample will be taken at time 0 (before FX06 application) and after 5, 15, 30, 60 min. Because FX06 in blood is quickly degraded by endopeptidases, the following sampling procedure should be followed: 1 ml blood to be collected into tubes containing Li-heparin, mixed by inversion 10 times, and then 0.8 ml of this blood to be transferred to test tubes containing 0.08 ml of 0.88 M HCl. It is critical that blood is being transferred to acid within 2 min of collection. The tubes are closed, the acidified blood samples will be mixed by inversion 10 times, and then processed to plasma by centrifugation (2500g; 10 min). Acidified plasma samples will be stored at a temperature of less than -20°C. FX06 dosage will be processed according by F4-Pharma, according to its dedicated procedure. Alternatively, pharmacokinetic study may be performed every other day of treatment (D1 to D5).

